STUDY PROTOCOL & ANALYSIS PLAN

Protocol Title: A Novel Parent Education Program for Early Intervention
Grant Number: 2U54GM104941-06
Clinical Trials ID: NCT04266717
Date of Document: September 15, 2022

Principal Investigator

Name: [name], PT, PhD
Department/Center: Physical Therapy Department, University of Delaware
Contact [contact]
Email Address: [contact]

PURPOSE

The purpose of this pilot clinical trial is to determine whether parent education impacts daily parent-infant handling and positioning activity or infants' developmental outcomes.

PARTICIPANTS

We will enroll twenty participants 1-5-months-old who are not yet rolling and are of any gender. To be included, infants and their parents must be able to safely and independently engage in the data collection activities and be available for data collections. Infants with medical equipment that restricts movement or positioning will not be included. Infants who are blind will also be excluded. Participants will be recruited via advertisement in the local community.

Participation in the study is voluntary and there is no compensation for participation. During the first contact made with potential participants, written information explaining the study will be provided that details in simple terms, a) criteria for participation, b) purpose of the research and procedures involved, c) right to withdraw at any time without penalty of any kind, and d) assurance of confidentiality (via number ID representation vs. name). If the individual meets the criteria for participation and is interested, the information just described will be reviewed, questions will be answered and an informed consent form will be signed in the presence of a witness. Parents of the participants will be reminded by the researcher that this signature does not bind them to participate and that they are free to withdraw at any time.

PROCEDURES

This study will involve 3 data collections that occur in the home. Informed consent will be obtained prior to the first data collection. Parents will be provided the opportunity to read the consent form, the contents will be reviewed with the family, and any questions or concerns will be discussed prior to obtaining consent.

After families consent, they will be asked to complete a Health & Demographic Form. Based on the information in this form, infants will be assigned to one of 4 risk categories: No health or socioeconomic risk; Only health risk; Only socioeconomic risk; or Health *and* socioeconomic risk. Health risk will include infants who were born very preterm, infants who had a documented neurologic or respiratory problem at birth, and infants who spent more than 1 week in the neonatal intensive care unit after birth. Socioeconomic risk will include infants whose families report combined income levels below poverty level or report middle or high school completion as the highest level of parental education. Blocked random assignment will then be performed within risk categories so that infants are assigned to the Milestone Education Group or the Positioning Education Group.

The total time commitment for participants in this study involves three data collections 30-75 minutes in duration; the baseline data collection happens at the time families enroll with infants at 1-5 months of age and the second data collection happens one month later. Families will also be asked to allow researchers to contact them monthly to collect milestone attainment data through the time infants begin walking independently (typically occurs between 10 and 18 months of age). The final data collection will happen when infants are between 16 and 24 months of age.

The first data collection will begin with infants donning the Get Around Garment, a smart garment that collects valid, reliable data about the position of infants (i.e., supine, reclined, upright, inclined, or prone). Then, the data collection will consist of: 1) one 2.5-minute *Structured Play Assessment* during which the infant will be placed by the experimenter for 15-30 seconds into each of the following 5 positions: supine, prone, inclined about 45 degrees from upright, reclined about 45 degrees from upright, and seated upright; 2) one 60 minute *Free Play Assessment* during which parents will be encouraged to go about their typical daily activities as if the experimenter were not there; and 3) a second 2.5-minute *Structured Play Assessment*. Accelerometer data from the garment will be collected simultaneously with video data throughout these assessments. Accelerometer data will be saved on a memory card or transmitted to a research computer via Wi-Fi. The entire visit will be video recorded. By comparing data from the garment and the video throughout the entire visit within each infant, we can determine whether the garment provides valid position data throughout the wearing session. The garment will be left with families, and they will be asked to have their infants wear it for 2 days during awake periods when with an adult but not during periods of sleep or periods without supervision. Families will be asked to log the times the sensor belt was worn and infants' general activity. Sensor data will be stored so we can better understand infants' activity across a typical 2-day period. We will leave 2 garments just in case one gets dirty. We will inform families they can wash the garments as they would typical clothing except that they should first remove the sensor unit. Note that garments that are in good condition (no stains) may be re-used for other babies after we wash them. After the 2-day period, the researchers will collect the garment from the family, will collect the Sensor Wearing Log and ensure the data on the log are complete and correct, and will ask parents to complete the Garment Perception Survey. They will also assess infants using the Alberta Infant Motor Scale and the Bayley Scales of Infant Development III to show their developmental abilities at the start of the study.

After the first data collection, parents will receive education in relation to their group assignment. The written information will be sealed in envelopes to ensure the assessor remains masked to group assignment. Participants will be reminded at each data collection not to discuss their group assignment of activities with the masked assessor. The Milestone Education Group will receive written information regarding developmental milestones expected based on the age of their infant. This information will be based on data from the Centers for Disease Control and Prevention (<https://www.cdc.gov/nccbdd/actearly/milestones/index.html>) and The American Academy of Pediatrics (www.healthychildren.org). This type of education will help parents understand the milestones that are typically observed at the their child's age and reflects the typical education parents receive. The Positioning & Play Education Group will receive written information regarding handling, positioning, and play activities they can engage in with their infants. These activities aim to provide infants safe opportunities to explore new ways of moving and controlling their bodies and interacting with objects to learn about their bodies and objects around them. These activities are safe and have been shown to advance development for typically developing infants when compared to a social control group that only involved parents talking to babies. The activities have not been tested in comparison to Milestone Education, which represents business as usual care. In addition, no one has previously been able to measure the impact of this type of education on everyday positioning practices by caregivers. The Get Around Garment will allow us to do that. Parents in both groups will be asked to provide their infants with opportunities to engage in the behaviors they have received education on for 20 minutes daily across 1 month. Parents will be informed that missing some days is acceptable

but they should try to engage in the activities as many days as possible. Parents will be asked to log their activities.

The second data collection will occur after a 4-week period of requested daily activity engagement according to the education received. The researchers will collect the Activity Logs and ensure data on them is complete and correct. Then the researchers will repeat all procedures from the first data collection, as described above, including a second, 2-day wearing period for the garment. Parents will be informed that daily activity engagement is no longer expected. At this data collection, parents will be taught how to keep track of their infant's milestones using the Milestone Checklist. The research team will contact families monthly through the onset of walking (typically between 10-18 months of age) to gather information about infants' performance on this checklist.

The third and final data collection will serve as a follow-up visit when infants are 16-24 months of age. Infants will be assessed using the Alberta Infant Motor Scale to show how their developmental abilities have changed since the start of the study and whether there are differences between the two education groups. Parents will be asked to complete the Dimensions of Mastery Questionnaire (DMQ 18) to evaluate each child's intrinsic motivation to move and explore so we can determine if and how this relates to our early measures of development and interaction.

RISKS AND BENEFITS

The risks associated with participation in this study are minimal. The assessment procedures are safe, and are similar to movement and play activities experienced by infants on a regular basis. The measurements are non-invasive, play- or functionally-based, and have been used in past research with infants.

There is a risk that participants may experience fatigue or be upset during the visits. If the infant cries or shows facial expressions suggesting fatigue or upset, we will take a break from the activities. We will not continue again until the infant has his/her needs met (sleeping, eating, diaper changing, etc) and appears happy and eager to join the testing again based on his/her affect and facial expressions. We will reschedule for another time if that better meets the infant's and family's needs.

The garment could be uncomfortable for infants. The sensor unit could rub the infant's skin. The garment has been designed with the sensor unit on the lateral aspect of the infant's trunk since infants do not typically place weight on this part of their body before they begin rolling over. Infants will not be enrolled in the study if they are already rolling. In addition, the sensor unit is quite small (2.44" long x 1.47" wide x 0.7" thick) so should not interfere with parents carrying infants. Researchers will check and parents will be asked to check infants' skin for redness after removing the garment. If we note irritation or redness that lasts more than 20 minutes, we will work on better fitting the garment and sensor. If the problem persists for an infant, we will discontinue that aspect of the experiment for that infant.

The sensor unit is made of small parts and uses a low level battery for energy supply. These parts could cause a choking risk if exposed. The garment is designed so that the sensor unit is secured within a 3D printed case, which is housed within a snug fabric enclosure to avoid small parts of the sensor unit from breaking off. As an added precaution, the garment will be used under the supervision of researchers or under the advised supervision of parents in the home.

Infants and parents may benefit from receiving education on development and learning the results of infants' developmental assessments.

Early handling, positioning, and play activities have been linked to future motor and cognitive abilities. It is helpful to understand the ways infants and parents are engaging in early movement activities and

how we can change those practices to positively impact development, especially for infants with health or socio-economic risks.

DATA ANALYSIS PLAN

All assessments and data coding will be conducted by trained experimenters masked to group assignment. Coders will be trained to ensure they are reliable before conducting official data coding. 20% of all data will be recoded to ensure high levels of intra- and inter-rater reliability are maintained. Double data entry will be conducted where applicable.

Primary outcome: To determine whether the change in AIMS score from Visit 1 to 2 differs between the two education groups, Wilcoxon tests will be performed for intra-group, Mann-Whitney for inter-group comparisons, with Bonferroni corrections.

Secondary outcomes:

To determine whether changes in parent-child interaction behavior or positioning practices (sensor data) differ from Visit 1 to 2 between the two education groups, Wilcoxon tests will be performed for intra-group, Mann-Whitney for inter-group comparisons, with Bonferroni corrections.

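### Infants are randomised within four risk categories but the between-group tests ignore them: the planned Mann-Whitney is valid, but loses some power if risk predicts AIMS change (minor)

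*Combined protocol and SAP*

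**What the plan says.** Under PARTICIPANTS the combined protocol and SAP sets the sample size: "We will enroll twenty participants 1-5-months-old". Under PROCEDURES, after consent and a health and demographic form, "infants will be assigned to one of 4 risk categories", formed by crossing health risk (yes/no) with socioeconomic risk (yes/no). Then: "Blocked random assignment will then be performed within risk categories".

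Under DATA ANALYSIS PLAN, the primary question is "To determine whether the change in AIMS score from Visit 1 to 2 differs between the two education groups". The named between-group method is "Mann-Whitney for inter-group comparisons, with Bonferroni corrections". The secondary outcomes (parent-child interaction and sensor-based positioning) get the same method. The risk categories appear in none of these analyses, and no reason for leaving them out is given.

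The plan gives no block size, alpha, effect size, power target or expected category sizes. It does not say how many tests the Bonferroni correction covers, or whether the Mann-Whitney is exact or approximate.

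**The concern.** Blocking within risk categories tends to balance risk between the two education groups. An unstratified Mann-Whitney takes its null variance from all 20 infants pooled, so it still counts variation between risk categories as noise. If risk predicts the one-month AIMS change, the test statistic varies less under the null than the test assumes. The test then rejects too rarely under the null, and it finds a real effect less often than an analysis that uses the two factors.

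What is at stake is forgone power in a very small trial, not false positives. Risk is recorded before assignment, so using it needs no new data.

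**Working it through.** **No figure to reproduce.** The documents state no power, alpha or effect size.

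**Inputs from the documents:** N = 20; two education groups; four risk categories from two yes/no factors; blocked assignment within category; outcome = AIMS change from Visit 1 to 2; unstratified Mann-Whitney.

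**Assumed inputs:** 1:1 allocation; blocks of 2 and 4; category sizes 5/5/5/5, 8/5/4/3, 12/3/3/2 and 14/3/2/1; effect 1.3 within-category SD; two-sided 5%; normal errors; both risks adding equally; no dropout. R² is the share of within-group variance in AIMS change explained by risk: 0, 0.05, 0.10 or 0.20. For scale, if half the infants have health risk and only that matters, the gap in mean change is 2√(R²/(1−R²)) = 0.46, 0.67 and 1.0 SD at R² = 0.05, 0.10 and 0.20.

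**Step 1: hand check of the conservatism.** With perfect balance on risk and a large-sample approximation, the true standard error is about √(1−R²) of the one the test uses, so the effective critical value is z/√(1−R²). The exact test has size of about 4.5% at R² = 0 because it is discrete, so z = 2.005.
- R² = 0.10: 2.005/√0.90 = 2.113, size 3.5%.
- R² = 0.20: 2.005/√0.80 = 2.241, size 2.5%.

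These lie close to the lower ends of the simulated ranges below. Incomplete blocks leave some imbalance, which raises the size.

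**Step 2: simulation** (40,000 trials per cell; ranges run over the four splits and both block sizes). The rank ANCOVA regresses the rank of the change on group, health risk and socioeconomic risk, and uses the model t-test for group.

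| R² | Exact Mann-Whitney size | Exact Mann-Whitney power | Rank ANCOVA power | Change v exact | Change v approximate | Change v unadjusted t-test on ranks |
|---|---|---|---|---|---|---|
| 0 | 4.4-4.6% | 74.0-74.8% | 73.5-75.5% | -0.8 to +1.1 | -1.8 to -0.3 | -3.1 to -1.8 |
| 0.05 | 3.9-4.5% | 71.9-72.7% | 73.1-75.4% | +1.2 to +3.1 | +0.1 to +1.6 | -1.5 to 0 |
| 0.10 | 3.4-4.0% | 69.5-70.2% | 73.2-75.0% | +3.3 to +5.3 | +2.0 to +3.5 | +0.5 to +1.9 |
| 0.20 | 2.6-3.7% | 64.3-65.0% | 72.4-74.5% | +7.8 to +10.0 | +6.5 to +8.2 | +4.6 to +6.4 |

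Changes are in percentage points. Rank ANCOVA size was 4.9-5.4%. The approximate Mann-Whitney is the normal approximation without continuity correction. The last column isolates the risk factors, because both analyses there use a t reference. Separate smaller runs gave like-for-like changes of +0.2 to +1.7 at R² = 0.10 and -3.6 to -1.7 at R² = 0; the 14/3/2/1 split did worst.

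**Step 3: does stratifying itself cost power?** No. Mann-Whitney power with stratified v unstratified randomisation was 69.6-70.7% v 68.7-69.9% at R² = 0.10 and 64.6-65.4% v 63.1-64.1% at 0.20. Size was 3.6-4.0% v 3.9-4.4% and 2.7-3.5% v 4.2-4.7%.

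**Step 4: sensitivity of the change v exact Mann-Whitney** (20,000 trials per cell; points at R² = 0.10, then 0.20).
- Effect 0.8 SD: +3.2 to +5.1; +6.6 to +9.5.
- Skewed errors: +3.0 to +4.1; +7.9 to +8.9.
- Only the double-risk category differs, so the model is misspecified: +1.0 to +3.3; +2.4 to +6.2.
- Alpha 0.05/3, one possible Bonferroni reading: +4.7 to +6.8; +9.7 to +12.5.

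**Step 5: sparse categories.** At 17/1/1/1 with both factors kept, rank ANCOVA loses 2.6-2.8 points v exact and 3.7-3.9 v approximate at R² = 0; at R² = 0.10 it gains 1.3-1.4 and 0.1. Each factor then has 1 + 1 = 2 infants at risk. A rule dropping factors with two or fewer infants at a level removes both, leaving an unadjusted t-test on ranks (76.5-76.7% v 74.0-74.3% exact at R² = 0). That last difference owes nothing to risk.

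**Step 6: why not a fully stratified test?** In a smaller run at R² of about 0.1, the van Elteren test had power 68.6-70.8% against 69.1-70.7% for the Mann-Whitney. Splitting 20 infants four ways uses up the gain.

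**The case against.** The strongest reply is that nothing planned is wrong. Stratifying for balance has its own purpose, this is a pilot, and there is no power target to miss. That stands.

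A reader might infer that leaving out the stratification factors makes the test invalid or inflates false positives. It does not: the error is in the conservative direction. Nor does stratifying lower Mann-Whitney power (step 3).

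A reader might also credit the whole 2 to 5 points at R² = 0.10 to using the risk factors. The table does not support that. Part of the difference comes from replacing a discrete or normal-approximation test with a t reference. Like for like, the risk factors give about 0.3 to 2 points at R² = 0.10, between -1.5 and 0 at 0.05, and a loss at 0. Likewise, much of the shortfall in size at R² = 0.10 is discreteness: the exact test starts at 4.4-4.6%, and stratification accounts for only about 0.3 to 0.4 points.

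Finally, the documents do not show that risk predicts a one-month AIMS change. RISKS AND BENEFITS speaks of "how we can change those practices to positively impact development, especially for infants with health or socio-economic risks", which is motivation and not evidence of prognostic strength. Also, "Participants will be recruited via advertisement in the local community", so sparse risk categories are plausible, and adjustment then gains little.

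What remains is a conditional loss of efficiency, and an analysis that drops a design factor without saying why.

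**Conclusion.** The point holds as a minor one. The analysis plan ignores the categories used for randomisation. If those categories predict AIMS change, the planned test is conservative and gives up power relative to an analysis with the two risk factors.

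Under the assumptions listed, switching to rank ANCOVA changes power by about -2 to +1 points at R² = 0, +2 to +5 at 0.10 and +6.5 to +10 at 0.20, the range depending partly on whether the Mann-Whitney is approximate or exact. The part due to risk itself is about -3 to -2, +0.3 to +2 and +4.6 to +6.4.

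A material gain therefore needs a strong link, such as the 1.0 SD gap corresponding to R² = 0.20. Confidence in the direction is good. The size cannot be fixed from the documents, because R², effect, block size, category sizes and alpha are all assumed.

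**What to change.** For the primary AIMS comparison, pre-specify a rank ANCOVA: rank the change score, regress the rank on education group, health risk (yes/no) and socioeconomic risk (yes/no), and use the model t-test for group. State that, before unmasking, a risk factor with two or fewer infants at one level is dropped. That threshold is a practical suggestion. Keep the unadjusted Mann-Whitney as a sensitivity analysis and say whether it is exact or approximate. The same model could serve the secondary outcomes, but the simulations do not cover sensor or interaction data. Alternatively, one sentence explaining why the risk categories are left out would close the gap in the plan.

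The cost is SAP wording and one regression per outcome, with no new data. If risk does not predict change, the price is about 1 to 2 points of power against the planned test (2 to 3 like for like). It is about 3 to 4 points against the planned test if nearly all infants fall in one category and no factor is dropped; the drop rule avoids that larger loss.

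### At Visit 2 the Activity Logs are checked before the primary-outcome AIMS is scored, and no stated masking step covers the log

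*Combined protocol and SAP*

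**What the plan says.** All references are to the combined protocol and SAP.

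- **Order at Visit 2** (PROCEDURES, second data collection): "The researchers will collect the Activity Logs and ensure data on them is complete and correct. Then the researchers will repeat all procedures". What is repeated is the first data collection, which includes the AIMS and the Bayley, done once the 2-day garment wear is over.
- **What the log holds** (PROCEDURES, education after the first data collection): parents in both groups are asked to "provide their infants with opportunities to engage in the behaviors they have received education on for 20 minutes daily", and "Parents will be asked to log their activities". The education differs by arm: milestone information in one, handling, positioning and play activities in the other.
- **Masking steps** (same part of PROCEDURES): "The written information will be sealed in envelopes to ensure the assessor remains masked to group assignment" and "Participants will be reminded at each data collection not to discuss their group assignment of activities with the masked assessor".
- **Masking commitment** (DATA ANALYSIS PLAN): "All assessments and data coding will be conducted by trained experimenters masked to group assignment".
- **Reliability check** (DATA ANALYSIS PLAN): "20% of all data will be recoded to ensure high levels of intra- and inter-rater reliability are maintained".
- **Endpoint** (DATA ANALYSIS PLAN): "Primary outcome: To determine whether the change in AIMS score from Visit 1 to 2 differs between the two education groups".

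Nowhere does the document say who handles the Activity Log, that it is sealed, or that it is checked after the AIMS.

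**The concern.** The stated order puts information that may identify the arm in front of the research staff shortly before the primary endpoint is scored. A log cannot be confirmed as complete and correct without being read, and clearing up a query may mean talking with the parent about what was done. The AIMS is scored by an examiner, so knowledge of the arm could influence the result.

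Only the Visit 2 score is exposed by this route, because the Visit 1 AIMS precedes both the education and the log. A scoring shift common to both arms cancels in the comparison; a shift that differs between arms would be read as an effect of education. If the same person also scores the AIMS at the final visit, what was learned from the log could carry over to that score.

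**Working it through.** The document gives no figure to reproduce here. The check is a reading of the visit sequence, followed by a hypothetical calculation that shows direction only.

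**1. Sequence.** At Visit 2 the log is collected and verified first; the Visit 1 procedures then follow, including the AIMS. The same generic term, researchers, is used for the people who check the log and for those who assess the infants. The text neither separates the two roles nor states that one person fills both.

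**2. Does any stated safeguard reach the log?**

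| Safeguard | What it covers | Covers a written log that staff read? |
|---|---|---|
| Sealed envelopes | Education materials given to parents | No |
| Reminder to parents | What parents say to the assessor | No; it limits conversation only |
| Masked-assessor statement | A commitment for all assessment and coding | No step is given for the log |
| 20% recoding | Rater reliability | No; recoding does not mask |

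**3. Hypothetical effect on the primary test.**

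Assumptions: 10 infants per group (20 enrolled, split equally; the ratio is not stated), no true effect, normally distributed change scores with SD 1, and an exact two-sided Mann-Whitney test. The plan gives neither alpha nor the number of Bonferroni comparisons, so three levels are shown: 0.05, 0.05/2 = 0.025 and 0.05/3 = 0.0167.

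With 10 v 10, U runs from 0 to 10 × 10 = 100 and is symmetric about 50 under the null. The exact size is 2 × P(U ≤ c), where c is the largest value that keeps the size within the level:

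- 0.05: reject if U ≤ 23 or U ≥ 77; size 0.0433
- 0.05/2: reject if U ≤ 20 or U ≥ 80; size 0.0232
- 0.05/3: reject if U ≤ 18 or U ≥ 82; size 0.0147

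If every score in one arm is shifted by δ SD more than in the other, the chance that a score from that arm exceeds one from the other is Φ(δ/√2): Φ(0.177) = 0.570 for δ = 0.25 and Φ(0.354) = 0.638 for δ = 0.5. Expected U therefore moves from 50 to 57.0 or 63.8. Simulated rejection rates (400,000 runs per case, Monte Carlo standard error at most 0.06 percentage points; no-shift row exact):

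| Scoring shift | 0.05 | 0.05/2 | 0.05/3 |
|---|---|---|---|
| None | 4.3% | 2.3% | 1.5% |
| 0.5 SD in both arms | 4.3% | 2.3% | 1.5% |
| 0.25 SD, one arm only | 7.2% | 4.2% | 2.8% |
| 0.5 SD in one arm, 0.25 SD in the other | 7.2% | 4.2% | 2.8% |
| 0.5 SD, one arm only | 16.1% | 10.5% | 7.6% |
| One arm, each score shifted 0.25 SD with probability 0.5 | 5.0% | 2.8% | 1.8% |
| One arm, each score shifted 0.5 SD with probability 0.5 | 7.0% | 4.1% | 2.7% |

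Only the difference in shift between arms matters. None of these shifts comes from the documents.

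**The case against.** The strongest reply is that the plan already requires every assessment to be masked and refers to a masked assessor as a distinct role. On that reading, a log check that unmasked the assessor would breach the plan, so someone else must do it. The reminder to parents also discourages talk about activities with the assessor, which leaves only silent reading of the log. The log's fields are unknown, and a record of days and minutes would reveal little. Visits are video recorded, so masked rescoring might be possible, and recoding 20% of all data would on its face include the AIMS. Finally, the experimenter is present for 60 minutes of free play before the AIMS, so closing the log route may gain little.

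Much of this stands as a limit. It means unmasking is not demonstrated, and the simulated rates say nothing about this trial. It does not close the gap. The masking statement is a commitment without a step for the log, and the protocol itself added sealed envelopes for the handout instead of relying on that commitment alone. Recoding addresses reliability, and the text does not say specifically that the AIMS is filmed or recoded. Free play is a separate route; leaving it open is no reason to leave this one open as well. Carry-over to the final visit is the most speculative part, since it needs the same assessor to remember one log until the infant is 16 to 24 months old.

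**Conclusion.** The point holds. The plan states an order in which possibly arm-revealing material is checked before the primary endpoint is scored, and no stated safeguard names that material. This should be fixed, with medium confidence, because it touches the primary outcome and costs almost nothing to correct.

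The size of any bias is unknown. It depends on three things the documents do not settle: whether the log's content identifies the arm, whether the person checking it also scores the AIMS, and whether that knowledge would shift scores differently between arms. The hypothetical range at the 0.05 level, from 5.0% to 16.1% against 4.3% with no shift, shows only what a differential shift of the assumed sizes would do. The case for the change rests on its low cost and not on those rates.

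**What to change.** Where PROCEDURES describes the second data collection, state that parents return the Activity Log in a sealed envelope, and that it is opened and checked only after the Visit 2 AIMS and Bayley have been scored and locked. The checker should preferably be an existing team member who does no outcome assessment or video coding; that also protects later video coding and the AIMS at the final visit. If a separate person already handles the log, one sentence saying so would largely resolve the point.

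Cost: one or two sentences of protocol text and 20 envelopes, one per family. There is no extra visit, no second staff member at the visit, and no change to the sample size or analysis. The downside is that log queries are settled a few days later, with slightly more recall error in the logs. The documents do not show whether a team member free of assessment and coding is available; without one, opening the log after scoring still protects the Visit 2 AIMS but not later coding or the final visit. For infants whose Visit 2 is already complete, the change can protect only later assessments. It closes the log route only and does not address what the experimenter may see during free play.

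### Does the third-visit AIMS comparison need its own written analysis when the plan's tests stop at Visit 2?

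*Combined protocol and SAP*

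**What the plan says.** The description of the third data collection in PROCEDURES fixes the timing: "The third and final data collection will serve as a follow-up visit when infants are 16-24 months of age". The AIMS at that visit is meant to show "how their developmental abilities have changed since the start of the study and whether there are differences between the two education groups".

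The DATA ANALYSIS PLAN contains two analysis statements. The primary one begins "To determine whether the change in AIMS score from Visit 1 to 2 differs between the two education groups". The secondary one begins "To determine whether changes in parent-child interaction behavior or positioning practices (sensor data) differ from Visit 1 to 2". Both use Wilcoxon tests within groups and Mann-Whitney tests between groups, with a Bonferroni correction whose family of tests is not defined. Neither mentions the third visit.

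PARTICIPANTS sets the age at entry and the size of the study: "We will enroll twenty participants 1-5-months-old who are not yet rolling and are of any gender". PROCEDURES gives the interval to the second visit: "The second data collection will occur after a 4-week period of requested daily activity engagement". The documents state no significance level, allocation ratio or power calculation.

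**The concern.** A group question that is stated in advance but has no stated analysis leaves room to choose the method after the data are seen. The sentence on the third visit can be read as comparing Visit 3 scores between groups or as comparing change from Visit 1. The Visit 1 to 2 rule also does not transfer without some thought. The first interval is about four weeks for everyone, whereas the interval to Visit 3 depends on age at entry and on where in the 16 to 24 month window the infant is seen. The claim at risk is the one about lasting effect: a positive result could have been selected, and a null one could be over-read. The monthly milestone data and the DMQ 18 have no written analysis either, although the documents state no between-group aim for them.

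**Working it through.** **What is fixed and what is open.** Set side by side, the two sections give this:

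| Element of the Visit 3 AIMS comparison | Stated? | Where |
|---|---|---|
| Instrument | Yes, AIMS | PROCEDURES |
| Age window | Yes, 16–24 months | PROCEDURES (twice) |
| Intent to compare the two groups | Yes | PROCEDURES |
| Between-group test | Not for Visit 3; Mann-Whitney for Visit 1 to 2 | DATA ANALYSIS PLAN |
| Contrast: Visit 3 score or change from Visit 1 | No | – |
| Rank and place in the Bonferroni family | No | – |

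The question is therefore prespecified and its method is not. The plan states no figure on this point, so there is none to reproduce.

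**Spread of the interval.** Shortest: 16 − 5 = 11 months. Longest: 24 − 1 = 23 months. Ratio: 23/11 = 2.1. These are the extreme corners. Infants are randomised within risk categories, so age at entry differs between groups only by chance. If visit timing is unrelated to group, the spread adds noise rather than bias.

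**Cost of leaving the contrast open.** Assumptions, none given in the documents:
- 10 infants per arm, a two-sided 5% level and no true effect.
- Normal scores, with ages uniform on 1–5 and 16–24 months.
- Correlation between visits, for the part of the score not due to age, of 0, 0.3 or 0.6.
- Age accounting for 0, 25% or 50% of score variance.
- Visit 1 SD equal to 0.5 or 1.0 times the Visit 3 SD.

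This makes 3 × 3 × 2 = 18 settings, with 20,000 simulated trials in each.

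- The exact Mann-Whitney test at 10 v 10 has an actual size of 4.3%.
- Either reading, chosen alone, is falsely significant in 4–5% of trials, including the settings with strong age effects. The age spread does not break the test.
- Taking the better of the two readings: 6–8%.
- The readings disagree in roughly 4% (0.063 × (1 − 0.35) = 0.041) to 8% (0.082 × (1 − 0.08) = 0.075) of null trials. Here 0.063 and 0.082 are the lowest and highest rates at which either is significant, and 0.35 and 0.08 the highest and lowest shares of those in which both are. Counting disagreements directly gave 4.0–7.6%.

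**Precision.** The 95% half-width for a difference in means, in SD units, is t(0.975, 2n − 2) × √(2/n). At n = 10 per arm this is 2.101 × 0.447 = 0.94. It describes a 20-infant trial. It would be the same for any standardised comparison of that size, at Visit 2 as much as at Visit 3, and a written Visit 3 analysis would not alter it.

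**The case for a change.** The strongest case for acting is that the remedy costs a sentence or two, and that small samples make analytic choices matter more.

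Two parts of this stand. First, the gap is real and nothing in the text closes it. Second, the two readings diverge more when there is a true effect: under the same assumptions they disagree in 10–23% of trials at a difference of 0.5 SD and in 16–36% at 0.8 SD. A reader of a Visit 3 result should know which contrast was used.

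Three parts do not carry the argument further.

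- A wider search, adding age-adjusted scores and interval-adjusted change, pushes the false-positive rate to 9–15%. The plan names only rank tests, however, and proposes no such adjusted models.
- It has been suggested that age at Visit 3 might depend on when the infant starts to walk, which would make age adjustment unsafe. The protocol ties the visit to age: "The final data collection will happen when infants are between 16 and 24 months of age". Walking marks the end of a different activity: "The research team will contact families monthly through the onset of walking". No statement links the two.
- A null Visit 3 result would indeed be too imprecise to show that an effect had gone. That follows from enrolling twenty infants, and choosing a contrast does not cure it.

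**Conclusion.** This is a documentation gap of minor importance, and no change to the plan is needed. The primary and secondary Visit 1 to 2 analyses stand as written, and no rule in the plan produces a wrong answer. Analysts would naturally carry the stated Mann-Whitney test to Visit 3, name the contrast used and treat the result as exploratory, as befits a follow-up visit outside the listed outcomes of a pilot. The choice between Visit 3 score and change from Visit 1 is open to judgement, and neither is shown to be better than the other here.

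If that choice were made after seeing the data, the error rate under no effect would rise from 4–5% to 6–8%. This assumes 10 per arm, a two-sided 5% level, roughly normal scores and visit timing unrelated to group. The text comparison is certain. The percentages are illustrations, since the documents give no SDs, correlations or allocation ratio.
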